² Subjects should be seated and resting for approximately 5 minutes prior to vital sign measurements - temperature, blood pressure, and heart rate. Tilt table may be used, if available.

³ Serum pregnancy test will be conducted in WOCBP (see section 5.5) at all scheduled visits. Urine pregnancy test will be performed on WOCBP (in addition to serum) at Baseline (within 24 hours prior to first dose).

CCI

CCI

⁶ One PK sample should be collected pre-dose and one PK sample should be collected post-dose. The time of the last BHV-3241/placebo dose prior to the sample collection and time of the PK sample collection and time of most recent meal should be reported on the CRF. At Weeks 4, 12, 24, 36 and 48, the morning dose of study drug should be held and administered in the clinic/office during the study visit, so that one pre-dose (trough) and one post-dose PK sample can be collected. The post-dose sample should be collected within a time window of approximately 2 to 4 hours. Collection of PK samples is not required at the Early Discontinuation visit.

CCI

⁸ Subjects should take the first dose of investigational product (IP) while in the office/clinic on the day of the Baseline visit and stay at the clinic for ~4 hours for observation. From start to end of Week 1, subjects will ingest either 300 mg QD of BHV-3241 or matching placebo QD. From start to end of Week 2, subjects will ingest either 300 mg BID of BHV-3241 or matching placebo BID. Starting with Week 3 and for the remainder of the double-blind portion of the study, subjects will ingest either 600 mg BID of BHV-3241 or matching placebo BID.

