Vital Signs ⁵	X	X				X	X	X	X
ECG (12-lead)	X			X if visit is conducted in person	X if visit is conducted in person	X	X	X	X
Laboratory Tests	X			X	X	X	X	X	X
Pregnancy Test ⁶	X			X	X	X	X	X	X
Sheehan Suicidality Tracking Scale	X		X			X	X	X	X
Adverse Event Reporting									
Monitor for Nonserious AEs and SAEs	X	X	X	X	X	X	X	X	X

Visit	Baseline Ext ¹ (Pre-dose)	Abbreviated Drug Dispensation Visit ²	2 Ext (phone)	3 Ext ⁷ (can be remote)	4 Ext ⁷ (can be remote)	5 Ext	6 Ext	7 Ext	8 Ext ⁸
Day (Visit procedures conducted within a +/- 7 day window, unless otherwise specified)	1		14	29	57	85	169	253	337
Week	0		2 Ext	4 Ext	8 Ext	12 Ext	24 Ext	36 Ext	48 Ext /Early Discontinuation ⁸
Efficacy Assessments									
Unified MSA Rating Scale Parts I-IV ³ (if visit is conducted remotely [by phone], only conduct Part I)	X					X	X	X	X
MSA Quality of Life	X					X	X	X	X
Time-to-event measures of disease progression	X					X	X	X	X
Dispense Study Drug	X	X				X	X	X	X
Study Drug Compliance Assessment	X		X			X	X	X	X
Under regular circumstances, visits are to be completed in-person, unless otherwise specified. Some visits can be conducted remotely, as needed, due to COVID-19 restrictions. See Protocol Section 4.3.1, COVID-19 Public Health Emergency, for further details and requirements regarding conduct of remote visits due to COVID-19.									
¹ Baseline visit for the OLE Phase is only required if there is an extended break (≥4 weeks) in dosing between the double-blind and OLE Phases. Otherwise, the double-blind Week 48 visit will take the place of the Baseline-Extension visit. Subjects should take the first dose of IP while in the office/clinic on the day of the Baseline-Extension visit and stay at the clinic for ~4 hours for observation. From start to end of Week 1-Extension, subjects will ingest 300 mg QD of BHV-3241. From start to end of Week 2-Extension, subjects will ingest 300 mg BID of BHV-3241. Starting with Week 3-Extension and for the remainder of the OLE, subjects will ingest 600 mg BID of BHV-3241.									

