² Abbreviated visit only needed for patients who completed dosing in the double-blind phase <4 weeks prior to entering the OLE Phase. The double-blind Week 48 Visit serves as the Baseline-Extension visit. This visit is primarily to dispense study drug. Subjects should take the first dose of IP while in the office/clinic on the day of the Baseline-Extension visit and stay at the clinic for ~4 hours for observation. From start to end of Week 1, subjects will ingest 300 mg QD of BHV-3241. From start to end of Week 2, subjects will ingest 300 mg BID of BHV-3241. Starting with Week 3 and for the remainder of the OLE, subjects will ingest 600 mg BID of BHV-3241.									
³ Including neurologic exam as a component of general physical exam and UMSARS.									
⁴ Height and weight.									
⁵ Subjects should be seated and resting for approximately 5 minutes prior to vital sign measurements - temperature, blood pressure, and heart rate. Tilt table may be used, if available.									

⁶ Serum pregnancy test will be conducted in WOCBP (see section 5.5) at all scheduled visits. Urine pregnancy test will be performed on WOCBP (in addition to serum) at Baseline-Extension (within 24 hours prior to first dose of open-label BHV-3241).

⁷ Week 4-Extension and Week 8-Extension are primarily to collect lab tests and, if conducted in the clinic/study site, to conduct an ECG. If the patient attends the visit at the clinic/study site, an assessment of adverse events, conduct of an ECG and collection of samples for lab analyses will be completed. If a participant prefers to not attend the visit at the clinic/study site, the lab samples can be collected/conducted at a local laboratory/location and a telephone call to confirm these were collected, as well to assess any adverse events, will take place.

⁸ Subjects who discontinue from study medication prior to Week 48-Extension will have an Early Discontinuation visit

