4.5.1 Open-Label Extension Phase Eligibility Criteria

The Investigator will be responsible for evaluating the participant's status, the participant's risk-benefit profile, the consent of the participant and the integrity of the trial, to determine whether a study participant is appropriate and eligible to continue participation in the optional OLE Phase, based on clinical judgement, the restricted and prohibited medication criteria specified in protocol section 5.4, the discontinuation criteria guidance specified in protocol section 6.4 and review of the following criteria:

- Completion of the 48 week Double-Blind randomized phase of the study. Participants who early-terminated from the double-blind phase of the trial or who discontinued the study medication for any reason will not be eligible for enrollment in the OLE phase. All participants must have their Week 48 visit in-person prior to enrolling in the OLE phase. Due to COVID-19, the timing of this visit may be delayed.
- Study participants must be:
 - able to continue to swallow whole study medication tablets
 - willing and able to continue to
 - adhere to the study drug regimen
 - to participate in all protocol specific assessments, and
 - to comply with the study visit schedule.
- Provide informed consent to participate in the OLE phase. All subjects who enter the OLE phase will sign a new informed consent form.

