4.5.2 Open-Label Extension Phase Procedures

When a site is open for recruitment to the OLE Phase, participants completing the double-blind treatment phase who choose to participate in the OLE phase and are eligible to continue, must consent to the OLE phase and directly enter the OLE phase starting at Week 48 visit of the double-blind treatment phase. The Week 48 visit will serve as the Baseline-Extension visit in the OLE phase for participants who move directly from the double-blind treatment phase to the OLE. Thereafter, participants will undergo visits at Week 2-Extension, Week 4-Extension, Week 8-Extension, Week 12-Extension, and then every 12 weeks of the OLE phase as outlined in [Table 2](#) (Schedule of Assessments & Events- Extension Phase).

A participant who has completed the double-blind treatment phase of the study prior to the OLE phase of the study being approved and open for recruitment at the study center where they are participating, can re-consent and start the OLE phase as long as the investigator determines that open-label treatment offers an acceptable risk-benefit profile for the participant. Once the study site is open for recruitment for the OLE, study participants who previously completed the double-blind phase of the study will have up to approximately 12 weeks (from the date of OLE opening at the site) to enroll and complete the OLE Baseline-Extension Visit, regardless of their date of double-blind phase completion.

For participants who have been off of the study drug for less than 4 weeks, the subject should attend an Abbreviated Drug Dispensation Visit at the investigative site, when medical and/or medication changes will be reviewed prior to dispensing open-label BHV-3241. In this case, for these participants, the Week 48 visit will also serve as the Baseline-Extension visit in the OLE Phase. Thereafter, participants will undergo visits at Week 2-Extension, Week 4-Extension, Week 8-Extension, Week 12-Extension, and then every 12 weeks of the Extension Phase as outlined in [Table 2](#) (Schedule of Assessments & Events- Extension Phase).

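### Table 2 contradicts itself on the pre-dose pregnancy test for subjects who enter the extension through the Abbreviated Drug Dispensation Visit

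*Protocol*

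**What the plan says.** Footnote 6 to Protocol Table 2 sets the rule for the extension: "Urine pregnancy test will be performed on WOCBP (in addition to serum) at Baseline-Extension (within 24 hours prior to first dose of open-label BHV-3241". Its preceding sentence calls for serum testing of women of childbearing potential at every scheduled visit. Section 6.2.2.4(d) repeats the urine test at Baseline-Extension before dosing, and otherwise leaves urine testing to the Investigator's discretion. SAP section 6.4.3 carries the same text.

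Footnote 2 describes the Abbreviated visit: "Abbreviated visit only needed for patients who completed dosing in the double-blind phase <4 weeks prior to entering the OLE Phase". It continues: "The double-blind Week 48 Visit serves as the Baseline-Extension visit. This visit is primarily to dispense study drug". It then places the first open-label dose on the day of the Baseline-Extension visit. Section 4.5.2 agrees on which visit counts: "In this case, for these participants, the Week 48 visit will also serve as the Baseline-Extension visit in the OLE Phase". It has medical and medication changes reviewed at the Abbreviated visit before open-label drug is handed out, and mentions no pregnancy test.

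In the Table 2 row "Pregnancy Test ⁶", there is a mark at Baseline-Extension, nothing at the Abbreviated visit, nothing at the Week 2-Extension phone visit, and a mark at every visit from Week 4-Extension on. SAP Appendix II shows the same pattern.

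In the double-blind schedule, Week 48 has a mark in the pregnancy-test row, which footnote 3 of Table 1 defines as serum. That footnote names a urine test only at the first baseline: "Urine pregnancy test will be performed on WOCBP (in addition to serum) at Baseline (within 24 hours prior to first dose".

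**The concern.** Footnote 6 fixes the urine test by two conditions at once: a named visit and a time limit before the first open-label dose. On the Abbreviated route these separate. The named visit is the earlier Week 48 visit, and the drug is dispensed later. A site working from the schedule cells would dispense at the Abbreviated visit without the pre-dose check that a footnote to the same table asks for.

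What is at stake is a safety check at re-exposure. For subjects randomized to placebo, this dose is their first exposure to the drug. Section 1.1.6 admits women of childbearing potential only if they are not pregnant at entry, and sections 6.4 and 8.1.6 require the drug to be stopped on pregnancy.

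**Working it through.** The documents give no figure to reproduce. The check sets the passages side by side and then does simple day arithmetic.

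**Step 1: which visit carries the test, by entry route**

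| Entry route | Visit counted as Baseline-Extension | Where the first open-label dose falls | Test marked at the dosing visit in Table 2? |
|---|---|---|---|
| Direct from Week 48 | Week 48 | Week 48 | Yes (Baseline-Extension column) |
| Off drug less than 4 weeks | Week 48 (earlier) | Drug dispensed at the Abbreviated visit | No (blank) |
| Off drug 4 weeks or more | Separate Baseline-Extension visit | That visit | Yes |

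Only the middle row has the test and the dose at different visits.

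**Step 2: is the blank cell a deliberate listing?** The Abbreviated column has marks for informed consent, concomitant medication, vital signs, adverse events and drug dispensing. The visit's procedures were therefore itemized, and the pregnancy test is not among them. Section 6.2.2.4(d) does not name the visit either.

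**Step 3: footnote 2 against itself.** It defines Baseline-Extension as the Week 48 visit and also puts the first dose on the day of Baseline-Extension. For a subject who attends the Abbreviated visit on a later date, that day has already passed.

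**Step 4: size of the gap.** Inputs:
- Break allowed on this route: less than 4 weeks (Protocol Table 2 footnote 2 and section 4.5.2), or up to and including 4 weeks (SAP sections 2.1 and 6.3).
- Last scheduled test before open-label dosing: the Week 48 test.
- Assumption: the last double-blind dose is taken on the day of the Week 48 visit. This fits sections 4.3.3 and 7.2.2, which have that morning's dose given in the clinic.

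Under that assumption, the days from last scheduled test to first open-label dose equal the days off drug:
- Protocol boundary: 4 × 7 = 28 days, strictly less, so at most 27 whole days.
- SAP boundary: at most 28 days.
- Limit in footnote 6: 24 hours, that is 1 day.

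The Week 48 test meets the limit only if open-label dosing starts within 24 hours of it. The Week 48 test that Table 1 defines is also serum, whereas footnote 6 asks for urine in addition.

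**The case against.** The best reply is that footnote 6 is part of the table. Its serum sentence covers every scheduled visit, and the Abbreviated visit is a column of that table. Footnote 6 also ties the urine test to 24 hours before the first open-label dose, so a careful site would test anyway, and section 6.2.2.4(d) lets the Investigator order one. Much of this stands: the defect is a cell and a visit definition that disagree with a footnote, not a missing safeguard. It does not remove the conflict. A serum test is not the 24-hour urine test, and a discretionary test is not a scheduled one. The serum sentence also cannot be taken literally across the columns, since the Week 2-Extension phone visit is blank too.

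The second reply is that very few subjects are involved. Under section 4.5.2, once a site is open its completers go straight into the extension at Week 48. The Abbreviated route therefore mainly serves those who finished shortly before their site opened. That is correct and limits the weight of the point.

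Three stronger readings are tempting, and the documents do not support them:
- **Direct rollovers also miss the urine test, because Table 1 names it only at the first baseline.** Section 4.5.2 makes Week 48 their Baseline-Extension visit. Table 2 marks the test there, and section 6.2.2.4(d) requires it before dosing.
- **Contraception can lapse, because section 4.5.1 bases extension entry on sections 5.4 and 6.4 but not 5.5.** Section 5.5 runs the duty through the study and to 30 days after the last dose of investigational product, and section 7.1.1 names the extension tablets as that product. A break under 28 days falls inside the 30 days. Subjects with longer breaks have a full Baseline-Extension visit with testing.
- **The whole interval up to the Week 4-Extension test is the gap.** The part after the first open-label dose is common to every entry route. Only the pre-dose part belongs to this one.

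**Conclusion.** The inconsistency is real and confined to one entry route. For subjects off drug for less than 4 weeks, Table 2 and its footnotes cannot all be followed as written when the Abbreviated visit falls on a later date than Week 48. The last scheduled pregnancy test can precede the first open-label dose by up to 27 days (28 under the SAP's boundary), where footnote 6 states 24 hours. The figure assumes that the last double-blind dose is taken at the Week 48 visit; a later or earlier last dose moves it accordingly.

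The number affected is small. They are women of childbearing potential, at least 40 years old at entry, on this route; the documents give no count. The point concerns safety scheduling in the extension only. It has no bearing on sample size, power or the primary analysis. A reader should not conclude that these subjects go untested, because a serum test is scheduled at Week 48.

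**What to change.** Reconcile the pregnancy-test row of Table 2, its footnotes 2 and 6, sections 4.5.2 and 6.2.2.4(d), and SAP Appendix II. They should state consistently how the requirement already in footnote 6 applies to the visit at which the first open-label dose is actually given. Footnote 2 should also stop placing the first dose on a day that, on this route, has passed. In the same edit, align the boundary of the break, which is below 4 weeks in the protocol and up to 4 weeks in SAP sections 2.1 and 6.3.

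How the conflict is resolved is for the sponsor and its clinical team. No new clinical rule or eligibility criterion is proposed here. The cost is a few text edits to the schedule and its cross-references, with no change to the statistical design or analysis.

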4.3.2 Screening Phase

The purpose of the Screening phase is to ensure that the appropriate subjects are entered into the trial and remain stable during the pre-treatment period. It is estimated that approximately 360 subjects will enter the Screening phase of the trial. The Investigator will determine that the subject meets eligibility criteria and will collect demographic and medical data presenting a full characterization of the subject. All attempts should be made to obtain medical and pharmacy records to confirm the subject's medical and medication treatment history. During Screening, Biohaven (or designee) may review relevant clinical information to confirm the diagnosis and subtype of MSA, for study eligibility and stratification prior to randomization.

Screening will range from a minimum of 1 day to a maximum of 42 days. Please refer to the Schedule of Assessments & Events (Table 1) for Screening procedure details.

If initial Screening lab sample results do not meet protocol-specified eligibility criteria and the Investigator determines that a repeat sample may meet the range required for eligibility, a repeat lab sample may be collected (one repeat collection/analysis allowed).

Rescreening: After obtaining Sponsor approval, a subject who does not meet protocol required eligibility criteria during Screening but who may potentially become eligible (e.g., logistical reasons such as exceeding screening window to accommodate time required for adjustment/stability of concomitant medication, washout of prohibited medication or repeat procedures to allow for recheck/confirmation of an abnormality that may meet the required range in a reasonable amount of time), may be entered as a Screen Failure in IWRS and then rescreened one time (entered as a Screen Failure and Rescreen in IWRS and eCRF). If the Sponsor approves Rescreening for a subject, instructions will be provided to the site regarding the specific Screening procedures/evaluations that will need to be repeated for Rescreening, as this is dependent on the amount of time elapsed.

4.3.3 Randomization Phase

Subjects who are determined to be eligible for the study will be randomized into the trial. It is estimated that approximately 325 subjects will be randomized and assigned to receive BHV-3241 (600 mg BID) or matching placebo (BID) in a 1:1 ratio, with randomization stratified by disease subtype of either MSA-P vs. MSA-C, diagnostic category of either possible MSA vs. probable MSA, and country.

Subjects should be administered the Day 1/first dose of study medication (300 mg QD or matching placebo QD) while in the office/clinic on the day of the Baseline visit. Subjects should stay at the office/clinic for monitoring for approximately 4 hours.

Dose titration period: For the rest of Week 1, subjects will ingest either 300 mg QD of BHV-3241 or matching placebo QD. From start to end of Week 2, subjects will ingest either 300 mg BID of BHV-3241 or matching placebo BID. Subjects should take the study drug twice a day; dosing in the morning and evening approximately 12 hours apart. If there is a delay in dosing, the interval between two doses should be no less than 6 hours.

An end of Week 2 assessment of compliance and tolerance to this dose titration schedule will be conducted. Per Investigator judgement, additional evaluations/procedures may be conducted at this timepoint as appropriate. If tolerability issues are experienced with 300 mg QD or 300 mg BID dosing, the titration schedule may be modified (see Section 7.2.3).

Full dose period: Starting with Week 3 and for the remainder of the study, subjects will ingest either 600 mg BID of BHV-3241 or matching placebo BID. Subjects should take the study drug twice a day; dosing in the mornings and evenings approximately 12 hours apart.

At Weeks 4, 12, 24, 36 and 48, the morning dose of study medication should not be taken on the day of the study visit until it is administered by site personnel during the study visit, so that one pre-dose (trough) and one post-dose PK sample can be collected approximately 2-4 hours post-dose (see Section 6.3.2).

The tablets should be swallowed whole with a drink of water. The tablets should not be split, chewed, or crushed.

Study medication can be taken without regard to meals, however, the last mealtime prior to collection of PK samples should be obtained.

If subjects have difficulty tolerating BHV-3241 600 mg BID, then the dose may be adjusted (see Section 7.2.3).

There is a +/- 3 day visit and procedure window during the study, unless otherwise specified. Please refer to the Schedule of Assessments & Events (Table 1) for details on procedures.

4.4 End of Treatment

Patients will have a Week 48/Early Discontinuation visit when they either complete the study at Week 48 or discontinue from study medication early (prior to Week 48). The Week 48/Early Discontinuation assessments/procedures should be conducted as an in person visit at the study site. Every effort should be made to conduct the Week 48 visit and maintain a +/- 7 day window. However, due to the COVID-19 public health emergency, if absolutely necessary, in order to minimize potential risks to study participant safety and to comply with governmental and local institutional guidance (e.g., study site has a policy that an in person clinical research visit must be delayed), the Week 48 visit window may be expanded beyond the +/- 7 day window up to an additional 12 weeks (maximum treatment duration of 60 weeks). However, every attempt should be made to conduct the visit as close as possible to the date that the visit is due. Under these circumstances, the Investigator should discuss the specific circumstances of these cases with the sponsor medical monitor (or designee), who must

approve the request to extend the treatment duration, prior to any modification of the visit window.

If the Week 48 visit window is modified, participants should have safety assessments evaluated remotely (e.g., via phone) and safety labs conducted (at a local lab) at the time of the scheduled Week 48 visit.

For subjects who discontinue early, depending on the reason for early discontinuation (e.g., declining patient status), some procedures (for example, PK samples, PD samples, lumbar puncture), may not be conducted at this visit. Conduct of all procedures, if possible, is encouraged. If possible, the subjects who discontinue from study medication prior to Week 48 should be contacted by a follow up phone call at the approximate time of their Week 48 visit, to collect information on clinical status (including Time to Event measures of disease progression, and if applicable, AEs, SAES).

